#### **IV. Participants:**

Describe the study participants and the population from which they will be drawn. Specify the inclusion and exclusion criteria. If you plan to include children, note their ages and whether you will include children in foster care. Note if the participants are particularly vulnerable in terms of cognitive limitations, education, legal migration status, incarceration, poverty, or some combination of factors.

Pregnant women attending the outpatient Obstetrics Department of HFH for antenatal care will be approached to determine interest in screening for possible eligibility and participation in the study. Women expressing interest will be asked to provide **consent for screening**, because our screening procedures include a formal assessment using the Hospital and Anxiety Depression Scale (HADS) (see inclusion criteria #6) and the depression component of the Structured Clinical Interview for DSM-5 (SCID) (see exclusion criteria #1). Those providing consent to be screened, will be assessed for eligibility to the intervention and enhanced usual care groups using the below inclusion and exclusion criteria:

- **Inclusion Criteria:**

1. ability to understand Urdu
2.  $\leq 22$  weeks' gestation
3. age  $\geq 18$  years
4. residence  $\leq 20$  km of Holy Family Hospital
5. intent to reside in the study areas until the completion of the study
6. score  $\geq 8$  on the HADS anxiety

- **Exclusion Criteria:**

1. Current major a depressive episode (MDE on SCID) or life-threatening health conditions including e.g. active severe depression or suicidal ideation
2. Self-reported past or current significant learning disability
3. Self-reported past or current psychiatric disorder (e.g. bipolar disorder or schizophrenia) or psychiatric care (e.g. current use of anxiolytic drug and/or other psychotropic drug)
4. medical disorders or severe maternal morbidity that require inpatient management that would preclude participation (e.g. eclampsia, pre-eclampsia, and antepartum hemorrhage)
5. ICU admission (indicated by diagnosis not admitted only for assessment)

For the healthy control group, unique to the biological substudy, inclusion and exclusion criteria will be as above, except that participants must score  $< 8$  on the HADS anxiety.

**NOTE:** If you are recruiting participants or receiving, accessing, or using data from a U.S. health care provider, HIPAA review is likely to be required. If you plan to bring identifiable health information from a foreign country to a U.S. covered entity (e.g., lab at the Hopkins SOM), HIPAA may be triggered. Check "yes" to the HIPAA question in the PHIRST application.

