This IRB application also covers a secondary study, to additionally study biological correlates of antenatal anxiety (i.e., immune and endocrine functioning) in a subset of women from the main trial: 200 drawn from our randomized trial (100 intervention, 100 usual care), as well as 100 healthy women without anxiety or depression. The aims of the secondary study are as follows:

**Aim 1:** To characterize the “immune phenotype” of anxious women across the peripartum, specifically by measuring the relation among anxiety symptoms and peripheral markers of inflammation (IL-6, CCL3, CXCL8, Eotaxin, VEGF, and GM-CSF, as supported by our preliminary data) within and across women (both anxious and healthy) and between those receiving the intervention and control.

**Aim 2:** To determine the relation between levels of allopregnanolone (ALLO) in pregnancy and 1) concurrent anxiety symptoms and 2) future symptoms of postpartum depression (PPD).

**Aim 3:** To examine the relation between changes in immune functioning (Aim 1) and ALLO levels (Aim 2) in anxious pregnancy across time.

**Aim 4:** To examine whether immune function and/or ALLO are mediators or moderators of the association between antenatal anxiety and poor birth outcomes (specifically, preterm birth and small-for-gestational age).

To supplement our study, we will collect qualitative data as part of a process evaluation to better understand women's experiences with the intervention (e.g. how it can be improved). Given the recent effects of COVID-19 on our participants and our study, we will also inquire about how the telephone format of our intervention is being received by our participants, as well as try to learn about the impact of social-distancing and other aspects of the COVID-19 situation on pregnant women generally.

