participants (e.g. to improve our intervention regarding this issue) we have also included some questions on this topic in our interview guide. If women have a lot to say and are tired or it is more convenient for them to do the interview in two telephone calls (one regarding questions on implementation of the intervention and the other on COVID-19) we will offer them to option to participate in two shorter interviews rather than one long one.

For the secondary biological study, we will be examining features of immune and endocrine system alteration in women enrolled in this trial to determine 1) whether there is a pattern of immune dysregulation common to women with antenatal anxiety 2) whether our intervention alters that pattern 3) whether immune dysregulation is related to dysregulation of allopregnanolone and 4) whether these biological mechanisms are mediators or moderators of the success of the intervention in reducing poor birth outcomes. We plan to recruit 300 pregnant women in three groups: 100 will from the intervention group, 100 will be from the enhanced usual care (EUC) group, and 100 will be healthy controls (pregnant women who have scored <8 on both anxiety and depression subscales of the HADS). Participants in the biological study will have their blood drawn at all four study visits; blood will be frozen as plasma at -80 and will be shipped to Johns Hopkins for immune and endocrine analyses.

- B. Provide a sample size and a justification as to how you arrived at that number. If you use screening procedures to arrive at a final sample a table may be helpful.

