### **Screening Procedures:**

As described briefly above, we will first approach all women to establish if they are  $\geq 18$  years old, reside within  $\leq 20$  km of Holy Family Hospital, intend to reside in the study areas until the study is complete, and understand Urdu to the HMHB. If they fulfill these demographic criteria, we will invite them to be screened in a private area about other exclusion criteria (e.g. their psychiatric history, history of psychiatric medications and history of a learning disabilities (See 100 Eligibility Screening Master Form, in Surveys/Instruments/Questionnaires in the Miscellaneous Section). If they are not excluded on this basis, these pregnant women will be further screened for having mild to high levels of anxiety on the HADS score  $\geq 8$  for anxiety by the research team member. As one of our exclusion criteria is a diagnosis of depression, the Structured Clinical Interview DSM disorders (SCID) module for Depression will also be used as a screening tool to rule out women with this diagnosis among those with a HADS score  $\geq 8$  for depression.

**Consent for Study Participation:** Women who ultimately screen eligible, will then be invited to participate in the main study. The staff person will indicate that based on the results of the screening the woman is eligible to participate, and she will give the pregnant woman a copy of the main study consent form (See 002 - Consent for Study Participation) and will go over the consent form with the woman, answering any questions she may have about the study. The woman will be approached first if possible and will be able to ask any questions, and/or take time to make a decision about participating. Although we are not asking husbands or other family members for consent, if there are family members present and the woman wishes for them to be present during the consent process we will comply with her wishes. We will describe and explain the study to both the woman and any accompanying family/friends. Women can decide at this point of contact to participate, or they may choose to take some time to make their decision (up to 14 days). If the latter option (i.e. delayed decision), our staff member will request a phone number to follow up with the

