The intervention (i.e. the HMHB sessions) will be provided by non-specialist providers, who will receive simplified training followed by regular supervision.(37) These trainers will have a university degree in the social sciences, at least one year of relevant work experience and knowledge of the local language, but no prior experience in mental healthcare delivery. During year one of the funded grant, they have received a six-day training. Further training will include practice in the field and regular group supervision. The data collection team ('assessors') and non-specialist providers ('trainers') will be continually monitored. During the training period, data collectors will be assessed for interrater reliability (IRR).

Enhanced Usual Care (EUC) Control Group: Women allocated to the control condition will receive EUC. The WHO recommends eight antenatal visits for a positive pregnancy experience(43) which we will be the target number of visits for EUC participants (depending on their gestational week). Visits will involve evaluating health status, discussing any concerns, and performing routine exams consistent with stage of pregnancy. For EUC medical staff at the hospital will receive additional mental health training. Transportation will also be provided or facilitated for participants to assist with attending appointments and up to two ultrasounds will be paid for by the study.

Healthy Controls (HC): For the purpose of this revised application we will add a 2nd control group of 100 women who have low or no anxiety or depressive symptoms (<8 on both the anxiety and depression sub-sections of the HADS). This will allow us to compare biological processes in a group of anxious women with the intervention, a group of anxious women without the intervention and compare them to these healthy controls (non-anxious or depressed, without the intervention).

All three Groups: All medical staff will be trained on the WHO Mental Health Gap Action Programme (mhGAP) curriculum on management and intervention for common mental disorders. Transportation will be reimbursed or provided for women in all three study arms and participants will be offered 400 rupees (\$4) or a mobile phone "top up" voucher of 400 rupees for participation. Participants will also be reimbursed the cost of ultrasounds indicated by their medical team at Holy Family Hospital.

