## Moderator Analysis

To examine potential effect modifiers of the intervention treatment effects on birth outcomes, we will expand the regression models to include a term for the interaction between intervention group status and the potential moderators (exposure to social support, stress levels, marital relationship and empowerment measured at baseline as well as retrospective report of IPV measured at 6 weeks postpartum). This will allow us to examine whether the effects of HMHB differ for mothers (or their children) with varying levels of the potential moderators; analyses will be informed by recommendations in Aiken and West (1991)(140) and Preacher et al. (2006) (141). This aim will be exploratory given limited power for detecting interaction effects.

5. **Answer the following if they are relevant to your study design:**

- If the study has different arms, explain the process for assigning participants (intervention/control, case/control), including the sequence and timing of the assignment.

Study statistician will produce a random sequence of assignments to the study arms. This sequence will be generated using a pseudo random-number generator, and will be constructed using randomly permuted blocks of size 4, 8, 12, and 16. The assignment list will be printed in order, with each step of the sequence separately stored in opaque envelopes and numbered sequentially. When an individual who has been determined as eligible via the screening procedure subsequently provides consent for study participation, the X will pull the next available envelope, opening it, and recording the assignment to intervention or control.

In addition to the participants randomized through the main study, there will be three arms for the biological study. We will choose the first 100 participants each in the intervention and control arms, and will also recruit a group of 100 healthy controls (HADS <8) who will participate only in the biological study.

- If human biospecimens (blood, urine, saliva, etc.) will be collected, provide details about who will collect the specimen, the volume (ml) and frequency of collection, how the specimen will be used, stored, identified, and disposed of when the study is over. If specimens will be collected for use in future research (beyond this study), complete the "Biospecimen Repository" section below.
-

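### Section IV admits healthy controls on HADS anxiety below 8 alone, while Section III.A and Study Implementation require below 8 on both HADS subscales; the definitions must be reconciled.

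*Combined protocol and SAP*

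**What the plan says.** Five places in the protocol describe the healthy-control group.

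- **Section I, aims of the secondary study:** "100 healthy women without anxiety or depression".
- **Section III.A, Study Design:** "100 will be healthy controls (pregnant women who have scored <8 on both anxiety and depression subscales of the HADS".
- **Section IV, Participants:** "For the healthy control group, unique to the biological substudy, inclusion and exclusion criteria will be as above, except that participants must score" below 8 on HADS anxiety. No HADS depression limit is given.
- **Section V, Study Implementation, Healthy Controls (HC):** "<8 on both the anxiety and depression sub-sections of the HADS". The same paragraph gives the purpose of the group as a comparator that is neither anxious nor depressed.
- **Section V, item 5, assignment to arms (after Moderator Analysis):** the study "will also recruit a group of 100 healthy controls (HADS <8) who will participate only in the biological study". No subscale is named.

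Two further provisions bear on depression. Exclusion criterion 1 in Section IV removes women with "Current major a depressive episode (MDE on SCID", and it carries over to healthy controls. Under Screening Procedures, the SCID depression module "will also be used as a screening tool to rule out women with this diagnosis among those with a HADS score" of 8 or more for depression.

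**The concern.** Section IV is the list that screening staff would normally apply. On its wording, a woman with few anxiety symptoms but raised depressive symptoms counts as a healthy control as long as she has no diagnosed episode. Under Section III.A and Study Implementation she does not.

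This group is the substudy's only non-anxious reference. The Aim 1 analysis compares immune markers in anxious women with those in healthy controls, and the Aim 3 analysis relates ALLO to immune markers by disease and intervention group. The Background cites a study linking low ALLO with concurrent low mood, so depressive symptoms in the reference group may bear on the markers being compared. If such women resemble the anxious groups on those markers, the contrast shrinks. Whatever the biology, a reader of the results could not tell which definition of healthy had been applied.

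**Working it through.** **1. The rules side by side.** Take a woman with HADS anxiety below 8, HADS depression of 8 or more, and no MDE on the SCID.

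| Place | Rule for controls | Eligible? |
|---|---|---|
| Section I | Free of anxiety and depression | No, on a natural reading |
| Section III.A | Both subscales below 8 | No |
| Section IV | Anxiety below 8, other criteria unchanged | Yes |
| Study Implementation, HC | Both subscales below 8 | No |
| Assignment paragraph | HADS below 8, subscale not named | Unclear |

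**2. Does another provision close the gap?** No. The carried-over exclusion and the SCID step remove a diagnosis. A HADS depression score of 8 or more sends the woman to the SCID, and she is ruled out only if the episode is confirmed.

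**3. Does the choice change the sample size?** No. The plan's enrolment reproduces: 180 / (1 − 0.40) = 300 in total and 60 / (1 − 0.40) = 100 per group. Neither definition alters it.

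**4. Illustration of possible dilution.** Section III.B gives 60 per group, four measures, correlation 0.6 and alpha 0.05. I take the test as two-sided on the mean of the four measures.

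- Variance factor: (1 + 3 × 0.6) / 4 = 0.7.
- 60 against 60: SE = sqrt(0.7 × 2/60) = 0.153.
- 60 against 120 (both anxious groups pooled): SE = sqrt(0.7 × (1/60 + 1/120)) = 0.132.

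At 0.5 SD, 60 against 60 gives 90.5% power, consistent with the plan's claim of at least 80%. At 0.3 SD the same calculation gives 50.2% (62.1% pooled), so it does not reproduce the lower end of the plan's range. That is a separate matter, and I use only the 0.5 SD case here.

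Let f be the share of controls with HADS depression of 8 or more, and r the degree to which their markers resemble the anxious group's (0 = not at all, 1 = fully). The observed difference is 0.5 × (1 − f × r). **Both f and r are assumptions; the documents give neither.**

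| f | r | Difference (SD) | Power, 60 v 60 | Power, 60 v 120 |
|---|---|---|---|---|
| 0 | any | 0.50 | 90.5% | 96.6% |
| 10% | 0.5 | 0.475 | 87.5% | – |
| 10% | 1 | 0.45 | 83.8% | about 93% |
| 20% | 0.5 | 0.45 | 83.8% | about 93% |
| 20% | 1 | 0.40 | 74.5% | 85.6% |

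Only the 20% share with full resemblance, in the unpooled comparison, falls below 80%.

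**The case against.** **The passages can be read together.** A woman below 8 on both subscales also satisfies Section IV, so nobody is forced to break one rule to follow another. Section IV introduces its list as being for the two randomized arms and adds healthy controls in a closing sentence. This makes an omission the likely explanation, but the sentence remains the formal criterion, and nothing in the documents says which text governs.

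**The group at issue is narrow.** Current MDE, active severe depression, suicidal ideation, psychiatric disorder and psychotropic use all remain excluded. The protocol also says that anxiety and depression often occur together, which suggests that few women would score low on one and high on the other. This stands, and it limits the reach of the point. A reader might infer that women with diagnosed depression could enter the healthy group; the exclusion criteria rule that out.

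**The size is not known.** A reader might infer a definite loss of power to below the 80% target. The documents do not support that. No share is given, and full resemblance to the anxious group is a worst case for women who by definition score below 8 on anxiety. Pooling the two anxious groups, which is reasonable at baseline although the plan does not state it, keeps power at about 86% or more throughout the illustration.

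**The analysis may absorb part of it.** The substudy plan adjusts for baseline severity and for confounders that differ between groups, and also treats anxiety as continuous. HADS depression is not named as a covariate, so this mitigates the problem without resolving it.

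**An anxiety-only definition is defensible.** The anxious groups have no HADS depression ceiling, so capping depression only in controls makes the contrast partly one of depression. That is a fair scientific argument, but the plan does not make it. Its stated purpose, in three places, is a comparator without anxiety or depression.

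**The postpartum depression model.** A reader might also infer that the healthy group is the reference for predicting postpartum depression. The Aim 2 analysis is a logistic regression on ALLO and anxiety trajectories and names no healthy reference group.

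**Conclusion.** The inconsistency is certain on the text and is not resolved elsewhere. Section IV admits women with HADS depression of 8 or more and no diagnosed episode; Section III.A and Study Implementation exclude them, and the assignment paragraph is ambiguous. Applied as written, Section IV could dilute the anxious-versus-healthy comparison of immune markers and ALLO. That consequence depends on how many such women are enrolled and how closely their markers resemble those of anxious women. The documents inform neither, so the power figures above are illustrative only.

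The matter is confined to a non-randomized comparator in the secondary biological study. The primary endpoint, the randomized comparison and the enrolment targets are untouched. It should still be corrected, because it is an operative eligibility rule and the correction is cheap.

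**What to change.** Amend the healthy-control sentence in Section IV to require a score below 8 on both HADS subscales, matching Section III.A, Study Implementation and the description in Section I. Replace the unspecified HADS limit in the assignment paragraph with the same wording.

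If any healthy controls were enrolled with HADS depression of 8 or more, identify them from their screening scores, report their number, and present a sensitivity analysis of the anxious-versus-healthy comparisons without them.

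The text change is one sentence and one parenthesis. No new assessment is needed, since Table 4 already schedules both HADS subscales at screening. The downside is slightly more exclusions when recruiting the 100 controls.

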## **V. Study Procedures:**

In this section, provide details of your procedures, particularly as they relate to human subjects. If this is a multi-center study, make the role of JHSPH clear. If the JHSPH will serve as **data coordinating center**, indicate in the sections below which procedures JHSPH will not be performing. Additional information regarding data coordinating centers is requested in a later section. If your study will develop in phases, address each item below by phase.

### **A. Recruitment Process:**

1. Describe how you will identify, approach, and inform potential participants about your study. Include details about who will perform these activities and what their qualifications are.

#### **Recruitment for Screening:**

Pregnant women will be recruited from the outpatient Obstetrics Department of HFH in Rawalpindi, Pakistan. A study poster containing information about the study will be displayed in the waiting area of the Obstetrics Department. The study poster will contain information about the HMHB trial and eligibility criteria for participation in the study (to solicit interest from literate women in the waiting area). As women check in to the obstetrics department, our research staff will be stationed with the hospital administrative staff. Our main recruitment strategy will involve female members of the assessment team based in the outpatient department who will establish minimum eligibility (based on inclusion criteria #1-5 in Section IV 'Participants' above: age>18, weeks of pregnancy ≤22, ability to understand Urdu, residence ≤ 20 km from HFH, and intention to remain there until the after delivery.) For pregnant women who self-report meeting these criteria (or that we have not already identified as not eligible based on their antenatal hospital record), they will describe and explain the 'HMHB study' to them and their families while visiting the obstetrics department and invite them to be screened for eligibility. Information will be provided in Urdu before any women are asked to provide written informed consent for the screening.

For more details, please see the sections below for a detailed description and the 'Screening Schema HMHB' uploaded in Miscellaneous documents.

